3.1.3.4. Serious Adverse Events

SAEs are collected throughout the study. The following variable will be derived:

• SAEs from Vaccination 1 throughout the study (for the 2 study groups).

3.2. SSB Primary Endpoint(s)

3.2.1. SSB Primary Safety Endpoints

The primary safety endpoints for Substudy B are the same as the primary safety endpoints for Substudy A (refer to Section 3.1.3), but the vaccine groups will be different.

The table below lists safety endpoints for Substudy B that will be derived and the more detailed derivations with the age groups of 50-64 years, 65+ years, and 50+ years will be applied.

Safety Endpoints	Vaccine Group (as Received)		
-	(RSVpreF + qIRV) 1.0-mL	(RSVpreF + qIRV) 0.5-mL	
Local reactions	Local reactions reported within 7 days	Local reactions reported within 7 days	
within 7 days	after vaccination with the combination	after vaccination with the combination	
after vaccination	(RSVpreF + qIRV) 1.0-mL at Visit B101.	(RSVpreF + qIRV) 0.5-mL at Visit B101.	
Systemic events	Systemic events reported within 7 days	Systemic events reported within 7 days	
within 7 days	after vaccination with the combination	after vaccination with the combination	
after vaccination	(RSVpreF + qIRV) 1.0-mL at Visit B101.	(RSVpreF + qIRV) 0.5-mL at Visit B101.	

DMB02-GSOP-RF02 7.0 Statistical Analysis Plan Template 31-Jan-2022 PFIZER CONFIDENTIAL TMF Doc ID: 98.03 Page 25 of 46

Safety Endpoints	Vaccine Group (as Received)		
	(RSVpreF + qIRV) 1.0-mL	(RSVpreF + qIRV) 0.5-mL	
AEs throughout the study	AEs reported from vaccination throughout the study among participants who received the combination (RSVpreF + qIRV) 1.0-mL at Visit B101.	AEs reported from vaccination throughout the study among participants who received the combination (RSVpreF + qIRV) o\0.5-mL at Visit B101.	
SAEs throughout the study	SAEs reported from vaccination throughout the study among participants who received the combination (RSVpreF + qIRV) 1.0-mL at Visit B101.	SAEs reported from vaccination throughout the study among participants who received the combination (RSVpreF + qIRV) 0.5-mL at Visit B101.	

The local reactions and systemic events in Substudy B will be the same as defined in Substudy A (Section 3.1.3.1 and Section 3.1.3.2) from Day 1 through Day 7 after vaccination, where Day 1 is the day of vaccination, with combination (RSVpreF + qIRV) 1.0-mL or combination (RSVpreF + qIRV) 0.5-mL. The vaccine groups are different from Substudy A and the derivations described in the above table.

3.2.1.1. Adverse Events

In Substudy B, AEs will be collected throughout the study. The following derivations will be included for each participant:

- 1. Any AE reported from vaccination throughout the study: If the AE started on the same day of vaccination and the AE start time is before the vaccination time, then this AE will not be counted. Otherwise, if the AE start time is missing or after the vaccination time, the AE will be included.
- 2. Any related AE reported from vaccination throughout the study: This is similar to the above except only the related AE is included (but excluding the related reactogenicity reported within 7 days of vaccination [Section 3.1.3]).
- 3. Any immediate AE reported after vaccination (AE start time is within 30 minutes after vaccination): Only those AEs that start on the same day of vaccination, and with nonmissing AE start time that is within 30 minutes of vaccination, will be included.
- 4. Any severe AE reported from vaccination throughout the study.
- 5. Any life-threatening AE from vaccination reported throughout the study.
- 6. Any AE leading to study withdrawal after vaccination.
- 7. Any SAE reported from vaccination throughout the study.
- 8. Any AESI from vaccination throughout the study, based on the AE PT.

The following events are considered AESIs:

- Confirmed diagnosis of influenza.
- Confirmed diagnosis of RSV infection.
- Confirmed diagnosis of myocarditis or pericarditis within 4 weeks after vaccination. See Section 3.6.3 for the evaluation of potential myocarditis or pericarditis.

Each of the above will be derived for the data presentation with 2 vaccine groups and the age groups of 50-64 years, 65+ years and 50+ years.

The same algorithm as stated in Section 3.1.3, for any AE reported in the CRF that was considered as reactogenicity during the clinical review and data-pooling process, this AE record will not be included in any of the derivations included in Section 3.1.3.3 and Section 3.1.3.4. However, if those reactogenicity AEs lead to discontinuation or were serious AEs, they will still be included in AE data.

3.3. SSB Secondary Endpoint(s)

3.3.1. SSB Secondary RSV Immunogenicity Endpoints

RSV A– and RSV B–neutralizing antibody titers will be determined on sera collected at all 2 visits. The RSV NTs measured at the Month 1 visit after vaccination in both combination groups are relevant to the secondary RSV immunogenicity endpoints.

Titers above the LLOQ are considered accurate and their quantitated values will be reported. Refer to Section 5.3.2 for LLOQ details. Titers below the corresponding LLOQ, or denoted as BLQ, will be set to $0.5 \times$ LLOQ for analysis. Missing assay results will not be imputed.

3.3.2. SSB Secondary HAI Immunogenicity Endpoints

HAI titers to the influenza strains will be determined on sera collected at all 2 visits. The immunogenicity results for HAI measured at the Month 1 visit after vaccination in both combination groups are relevant to the secondary HAI immunogenicity endpoints.

Titers above the LLOQ are considered accurate and their quantitated values will be reported. Refer to Section 5.3.2 for LLOQ details. Titers below the corresponding LLOQ, or denoted as BLQ, will be set to $0.5 \times$ LLOQ for analysis. Missing assay results will not be imputed.

3.4. SSA and SSB Other Endpoint(s)

3.4.1. SSA and SSB Use of Antipyretic Medication Within 7 Days After Vaccination

The derivation for the use of antipyretic medication would be the same for both Substudy A and Substudy B.

The use of antipyretic medication within 7 days after vaccination is collected via the e-diary. The derivation will be similar to local reactions and systemic events, except there is no severity grading and the only data source will be from the e-diary.

3.4.2. SSA and SSB Exploratory Endpoints

In addition to the endpoints included in Section 3.1.1, Section 3.1.2, and Section 3.1.3, the following variables will be derived for exploratory endpoints for each participant.

3.4.2.1. RSV A- and RSV B-Neutralizing Antibody Titers

RSV A– and RSV B–neutralizing antibody titers will be determined using the same method for both Substudy A and Substudy B at all eligible visits.

Titers above the LLOQ are considered accurate and their quantitated values will be reported. Refer to Section 5.3.2 for LLOQ details. Titers below the corresponding LLOQ, or denoted as BLQ, will be set to $0.5 \times$ LLOQ for analysis. Missing assay results will not be imputed.

RSV A and RSV B NTs at each blood sampling time point are included in the assay result data, thus no derivation is needed. The following variables will be derived for each participant:

- 1. RSV A/B at each blood sampling time point: This will be derived as the geometric mean of RSV A and RSV B NTs measured at each blood sampling time point for each participant.
- 2. RSV A, RSV B, and RSV A/B NT fold rise: This will be derived from before vaccination to each applicable blood draw visit after vaccination. The numerator is the postvaccination value and the denominator is the prevaccination value. The RSV A/B NT fold rise is derived as the geometric mean of the RSV A NT fold rise and the RSV B NT fold rise.

For Substudy A: For combination RSVpreF + qIRV, assay results at Visit A101 will be used as before vaccination. For the sequential-administration group, assay results at Visit A102 will be used if both Visit A101 and Visit A102 data are available; otherwise, the assay results at Visit 1 will be used if only Visit 1 assay results are available.

When calculating a fold rise, if assay results are < LLOQ, the assay results will be converted to $0.5 \times LLOQ$, except when the prevaccination assay result is < LLOQ while the postvaccination result is \geq LLOQ, in which case the prevaccination value will be set to LLOQ.

DMB02-GSOP-RF02 7.0 Statistical Analysis Plan Template 31-Jan-2022 PFIZER CONFIDENTIAL TMF Doc ID: 98.03 Page 28 of 46

3.4.2.2. HAI Titers

For both SSA and SSB: HAI titers to the influenza strains in combination RSVpreF + qIRV or qIRV alone will be determined on sera collected at the 1st visit and the 2nd visit.

The fold rise on HAI titers will be derived for each influenza strain. Similar to NTs, when calculating a fold rise, if assay results are < LLOQ, the assay results will be converted to $0.5 \times LLOQ$, except when the prevaccination assay result is < LLOQ while the postvaccination result is \geq LLOQ, in which case the prevaccination value will be set to LLOQ.

3.4.2.3. HAI Seroprotection

For both SSA and SSB: HAI seroprotection is defined as an HAI titer \geq 1:40. This will be derived for each participant for each strain at the 1st visit and 2nd visit.

3.4.2.4. HAI Seroconversion

For both SSA and SSB: HAI seroconversion from before the 1st visit to 1 month after qIRV administration (2nd visit) will be defined for each participant for each strain as follows.

- 1. If the HAI titer is <1:10 before qIRV administration, seroconversion is achieved if the postvaccination titer is ≥1:40.
- 2. If the HAI titer is ≥1:10 before qIRV administration, seroconversion is achieved if the fold rise in titer from before qIRV administration to after vaccination is ≥4.

3.5. Baseline Variables

Substudy A and Substudy B use the same derivation for the following baseline variables.

3.5.1. Baseline Definition

Day 1 is defined as the day of Vaccination 1. Measurements or samples collected prior to Vaccination 1 on Day 1 are considered the baseline data for the assessments.

3.5.2. Demographics, Baseline Vital Signs, and Medical History

The demographic variables that will be collected include sex, race, ethnicity, and date of birth. Age at the time of vaccination (in years) will be derived based on birthday. For example, if the vaccination date is 1 day before the participant's 86th birthday, the participant is 85 years of age.

Medical history of clinical significance will be collected and categorized according to the current version (at the time of reporting) of MedDRA.

Baseline blood pressure and pulse rate will be collected.

Participants' receipt of the most recent licensed influenza vaccination for the 2022-2023 northern hemisphere season, or the 2022 southern hemisphere season relative to study intervention, will be categorized as >120 days before study intervention administration and <=120 days before study intervention administration for SSA.

For SSB, the criteria will be changed to >180 days before study intervention administration and <=180 days before study intervention administration for latency categorization.

3.5.3. E-Diary Completion

An e-diary will be considered transmitted if any data for the local reactions and systemic events are present for any day. If all data are missing for all items (local reactions and systemic events) on the e-diary for all 7 days after vaccination, then the e-diary will be considered not transmitted. An e-diary will be considered transmitted for a given day if any data are present for that day. The following variables will be derived:

- e-diary data transmitted at both Day 1 and Day 2.
- e-diary data transmitted from Day 1 to Day 3.
- e-diary data transmitted from Day 1 to Day 4.
- e-diary data transmitted from Day 1 to Day 5.
- e-diary data transmitted from Day 1 to Day 6.
- e-diary data transmitted for all 7 days.

3.5.4. Nonstudy Vaccines

Any nonstudy vaccinations received from 28 days prior to study enrollment through the conclusion of study participation will be collected.

Nonstudy vaccinations will be categorized according to the latest version (at the time of reporting) of the WHODrug Dictionary.

Refer to Section 3.5.2 for latency categorization in licensed influenza vaccine receipt.

3.6. Safety Endpoints

3.6.1. Adverse Events

Guillain-Barre syndrome (from Day 1 through Day 43 after vaccination with RSVpreF or (RSVpreF+qIRV), where Day 1 is the day of vaccination), atrial fibrillation (from vaccination with RSVpreF or (RSVpreF+qIRV) through the Month 1 visit), and polyneuropathy (from Day 1 through Day 43 after vaccination with RSVpreF or (RSVpreF+qIRV), where Day 1 is the day of vaccination) have been identified as Tier 1 events for RSVpreF. The RSV program list of Tier 1 MedDRA PTs, maintained by the safety risk lead, is in the CAETeLiSt and is referenced in the safety surveillance review plan for the program. The current list of Tier 1 events should be confirmed to ensure that appropriate Tier 1 events will be used to produce final tables/graphs before conducting an analysis. Because RSVpreF is a vaccine component of the combination vaccine and is also study vaccine, these Tier 1 events are defined in this study.

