8.4.1. Time Period and Frequency for Collecting AE and SAE Information

The time period for actively eliciting and collecting AEs and SAEs ("active collection period") for each participant begins from the time the participant provides informed consent, which is obtained before the participant's participation in the study (ie, before undergoing any study-related procedure and/or receiving study intervention), through and including the last study visit.

Follow-up by the investigator continues throughout the active collection period and until the AE or SAE or its sequelae resolve or stabilize at a level acceptable to the investigator.

When a clinically important AE remains ongoing at the end of the active collection period, follow-up by the investigator continues until the AE or SAE or its sequelae resolve or stabilize at a level acceptable to the investigator and Pfizer concurs with that assessment.

For participants who are screen failures, the active collection period ends when screen failure status is determined.

If the participant withdraws from the study and also withdraws consent for the collection of future information, the active collection period ends when consent is withdrawn.

If a participant permanently discontinues or temporarily discontinues study intervention because of an AE or SAE, the AE or SAE must be recorded on the CRF and the SAE reported using the Vaccine SAE Reporting Form.

Investigators are not obligated to actively seek information on AEs or SAEs after the participant has concluded study participation. However, if the investigator learns of any SAE, including a death, at any time after a participant has completed the study, and they consider the event to be reasonably related to the study intervention, the investigator must promptly report the SAE to Pfizer using the Vaccine SAE Reporting Form.

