10.9.10.6.3. Visit A103 - Follow-Up Visit (28-35 Days After Vaccination 2)

- Record any nonstudy vaccinations received since the last study visit as described in Section 10.9.8.7.
- Review concomitant medication use and record any medications that are prohibited, as described in Section 10.9.8.7.1.
- Collect a blood sample of approximately 50 mL for immunogenicity.
- Review the e-diary data and obtain stop dates for any ongoing events recorded on the last day of e-diary completion for the previous period.
- Record AEs and SAEs as described in Section 10.3.3 and obtain and record stop dates for previously reported events.
- Collect the sponsor-provisioned e-diary or assist the participant with removing the study
 application from his or her own personal device. Ensure that all data have been
 transferred before deactivating the e-diary or deleting the app.
- Complete the CRF and source documents.

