Blood will be collected prior to vaccination and at the final study visit.

Local reactions and systemic events occurring within 7 days after vaccination will be recorded in an e-diary device or smartphone application.

AEs and SAEs will be collected from the signing of informed consent through study completion.

This study will have stopping rules that will apply to participants as specified in Section 10.10.10.5 with monitoring by designated unblinded sponsor site staff on an ongoing basis. If a stopping rule is confirmed, further randomization and administration of study intervention will be paused while additional information is gathered, and cumulative unblinded safety data will be reviewed by the IRC. Participants who have received study vaccination will continue further study visits and procedures as scheduled. A charter for the IRC will be prepared and finalized before the first participant provides informed consent.

Safety data accumulated at least 1 week following vaccination in each group will be reviewed by the sponsor's IRC to inform further development. Based on review of safety or immunogenicity data of any study intervention group, at Pfizer's discretion, subsequent collection of blood samples from participants in that group may be halted and/or not analyzed and study visits or other procedures may be discontinued.

In the event that Substudy B is conducted immediately prior to or within the influenza season, SIIV will be offered to participants at the end of their study participation.

The total duration of Substudy B for each participant will be up to approximately 1 month. The total duration of Substudy B based on the approximate 1-month enrollment period will be approximately 2 months.

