10.10.10.6.2. Visit B102 - Follow-Up Visit (28-35 Days After Study Vaccination)

- Record any nonstudy vaccinations received since the last study visit as described in Section 10.10.8.7.
- Review concomitant medication use and record any medications that are prohibited, as described in Section 10.10.8.7.1.
- Collect a blood sample of approximately 50 mL for immunogenicity assessments.
- Review the e-diary data and obtain stop dates for any ongoing events recorded on the last day of e-diary completion for the previous period.
- Record AEs and SAEs as described in Section 10.3.3 and obtain and record stop dates for previously reported events.
- Collect the sponsor-provisioned e-diary or assist the participant with removing the study
 application from his or her own personal device. Ensure that all data have been
 transmitted before deactivating the e-diary or deleting the application.
- Complete the CRF and source documents.

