2.3. Study Design

2.3.1. Substudy A

This is a Phase 1b, parallel-group, randomized, placebo-controlled, observer-blinded substudy. Approximately 250 healthy adults ≥ 60 years of age will be randomized 1:1 to either:

- Group 1: combination (RSVpreF + qIRV) (Visit A101) followed by placebo (Visit A102) or
- Group 2: sequential administration of qIRV (Visit A101) followed by RSVpreF (Visit A102) administered 1 month apart.

Randomization will be stratified by 3 age groups (60 to 64, 65 to 79, and \geq 80 years) within each study site. There are 3 scheduled study visits each 1 month apart. To assess immunogenicity, blood samples will be collected prior to vaccination at Visit A101 (Day 1) and Visit A102 (Month 1), and at Visit A103 (Month 2).

Local reactions (redness, swelling, and pain at the injection site) and systemic events (fever, headache, fatigue, nausea, vomiting, diarrhea, chills, new or worsened muscle pain, and new or worsened joint pain) occurring within 7 days after each vaccination visit (Visit A101 and Visit A102) will be recorded in an e-diary device or smartphone app.

AEs and SAEs will be collected from the signing of the informed consent through Visit A103.

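### Tier 1 events: the Day 43 window for Guillain-Barre syndrome and polyneuropathy outruns active follow-up for about 325 of 450 recipients, and the asymptotic p-value and CI are unreliable at very low counts

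*SAP*

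**What the plan says.** SAP 3.6.1 names three Tier 1 events for RSVpreF. Two have a 43-day window: "Guillain-Barre syndrome (from Day 1 through Day 43 after vaccination with RSVpreF or (RSVpreF+qIRV), where Day 1 is the day of vaccination" and "polyneuropathy (from Day 1 through Day 43 after vaccination with RSVpreF or (RSVpreF+qIRV), where Day 1 is the day of vaccination". The third, atrial fibrillation, is counted only to the Month 1 visit, which fits the visit schedule.

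Protocol 8.4.1 has active AE and SAE collection run from consent "through and including the last study visit". SAP 2.3.1 repeats this for Substudy A: "AEs and SAEs will be collected from the signing of the informed consent through Visit A103". Visit A103 is headed "Follow-Up Visit (28-35 Days After Vaccination 2" and Visit B102 is headed "Follow-Up Visit (28-35 Days After Study Vaccination". Protocol 10.10.6.1 adds for Substudy B: "The total duration of Substudy B for each participant will be up to approximately 1 month". Once a participant has completed the study, Protocol 8.4.1 requires a report "if the investigator learns of any SAE, including a death, at any time after a participant has completed the study" only when the investigator also considers the event reasonably related to study intervention.

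SAP 6.5.1 pools everyone in both substudies who received RSVpreF or the combination and compares them with the placebo arm of C3671013. It specifies a Miettinen-Nurminen 95% CI for the difference in percentages and an asymptotic normal p-value from the same statistic. From C3671013 it promises only a count per event and a denominator. The same section describes safety analysis as generally exploratory.

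**The concern.** There are two separate problems in one table.

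First, a percentage labelled through Day 43 implies that recipients were observed that long. Most are scheduled to leave the study one to two weeks earlier. Nothing in the planned output would show or correct for this.

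Second, the two groups differ in size by a factor of about 40, and at low event rates the expected count in the smaller group is well below one. A normal approximation to a score statistic cannot be trusted there. A single chance case could be printed with p below 0.05, and with a CI excluding zero, where exact methods do not support that reading. This is the only between-group p-value in the SAP, and it concerns serious neurological events, so it is likely to be read closely.

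**Working it through.** The documents give no sample size, rate or p-value for the Tier 1 analysis, so there is no planned figure to reproduce.

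**Inputs**
- Substudy A: about 250 participants, 125 per group (Protocol 10.9.6.1). Substudy B: about 200 (Protocol 10.10.6.1). Pooled recipients: 250 + 200 = 450.
- C3671013 placebo: Protocol 2.2.3.1 gives over 37,000 randomized 1:1. Assumed about 18,500; 18,000 to 20,000 checked.
- No alpha is stated for the p-value. Two-sided 0.05 is assumed, from the 95% CI.
- Event rates are not given. Values of 1e-4 and 2e-4 per 43-day window are assumptions.

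**Window**

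With Day 1 as the vaccination day, a visit 28 to 35 days later falls on Day 29 to 36.
- Substudy A Group 1 receives the combination at A101. A103 follows a second (placebo) injection, so it falls 56 to 70 days later, Day 57 to 71. The window is covered.
- Substudy A Group 2 receives RSVpreF at A102, so its last visit is Day 29 to 36 after RSVpreF.
- Substudy B has one injection, so its last visit is Day 29 to 36.

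Share not scheduled to Day 43: (125 + 200)/450 = 72%. This is a share of recipients, not of events.

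Person-days observed out of 450 × 43 = 19,350:
- last visit at Day 29: 125 × 43 + 325 × 29 = 14,800 (76.5%)
- last visit at Day 36: 125 × 43 + 325 × 36 = 17,075 (88.2%)

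Expected events missed are 12% to 24% under a constant hazard. If the hazard falls linearly to zero at Day 43, the captured share is (125 + 325 × (1 − ((43 − d)/43)²))/450, which is 92.3% at d = 29 and 98.1% at d = 36, so 2% to 8% are missed.

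In cases, at constant hazard, 450 × r × (0.118 to 0.235) gives 0.005 to 0.011 at r = 1e-4 and 0.011 to 0.021 at r = 2e-4.

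**p-value**

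The asymptotic p uses z = (p1 − p0)/√[p(1 − p)(1/n1 + 1/n0) × N/(N − 1)], with p the pooled proportion, two-sided normal. Mid-p is the two-sided Fisher p minus half the hypergeometric probability of the observed table. The last column is twice the one-sided exact unconditional p based on the same score statistic, maximised over the common rate. For 1 event in 450 against x in 18,500:

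| x | Asymptotic | Mid-p | Fisher | Exact unconditional, doubled |
|---|---|---|---|---|
| 0 | 1.4e-10 | 0.012 | 0.024 | 0.018 |
| 1 | 9.7e-6 | 0.024 | 0.047 | 0.041 |
| 2 | 0.0004 | 0.036 | 0.070 | 0.066 |
| 3 | 0.003 | 0.047 | 0.092 | 0.093 |
| 4 | 0.010 | 0.059 | 0.113 | 0.121 |
| 5 | 0.021 | 0.071 | 0.134 | 0.149 |
| 6 | 0.038 | 0.083 | 0.155 | 0.178 |
| 7 | 0.060 | 0.095 | 0.175 | 0.207 |

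At 0.05, Fisher and the doubled exact p contradict the asymptotic verdict at 2 to 6 placebo events, and mid-p does so at 4 to 6. At 0 and 1 all four are below 0.05, but the asymptotic value is far too small. With 2 events in 450, Fisher disagrees at 14 to 21 placebo events and mid-p at 19 to 21.

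The CI follows the p-value. Per 10,000:
- 1 vs 2: Miettinen-Nurminen 2.7 to 124; exact unconditional −0.3 to 120
- 1 vs 5: Miettinen-Nurminen 0.9 to 122; exact unconditional −2.0 to 117

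**Sensitivity.** The upper cut-off moves with the assumed sizes: 1 vs 7 gives asymptotic p = 0.047 with 20,000 placebo recipients and 0.041 with 400 study recipients. Placebo sizes of 18,000 and 19,000 leave the range of disagreement with Fisher at 2 to 6.

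**Long-run behaviour.** Enumerating binomial outcomes under a common rate, the asymptotic test rejects at most 4.4% of the time for rates up to 1e-4, peaks at 8.9% near 2.8e-4, and is at 5.5% at 5e-4. The probability of no event in 450, (1 − r)^450, is 96% at 1e-4 and 91% at 2e-4.

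**The case against.** The strongest defence is that little hangs on this. SAP 6.5.1 presents the analysis as exploratory, SAP 5.1 states no hypothesis, and neither substudy's stopping rules use this p-value. No event at all is the most likely result at the assumed rates. The asymptotic test is not inflated at or below 1e-4, and the chance of one event together with 4 to 6 placebo events is about 0.5% at 1e-4 and 3.5% at 2e-4. The expected number of missed cases is a few hundredths at most. All of this stands, and it limits the consequence to reporting.

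It is also fair that collection does not shut completely at the last visit. Protocol 8.4.1 and 8.4.3 continue follow-up of events already under way until they resolve or stabilise, so symptoms that began before the last visit and were diagnosed later can still be captured. A late visit, or a related SAE that the investigator learns of afterwards, can bring in later onsets. The gap concerns onsets after the last visit.

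A further argument is that one sentence disclosing the number followed to Day 43 would do. It would cure the label, but would leave the groups compared over windows that may differ, and would leave the p-value and CI as they are.

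Three stronger readings are tempting but not supported:
- That 72% of cases are lost. The 72% counts recipients; the expected loss of cases is 2% to 24%, depending on the hazard.
- That the comparison is biased towards the vaccine. The documents do not give C3671013's follow-up, so neither the direction nor the size of any bias is known.
- That any single event with 6 or fewer placebo events gives a false positive. At 0 or 1 placebo events the exact methods are also below 0.05; only the size of p is wrong.

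**Conclusion.** The point holds, with small and exploratory consequences. The window conflict follows from the two documents alone: about 325 of 450 planned recipients are not actively followed to the end of the window in which they will be counted. The 325 is a planned figure. Early withdrawals from Substudy A Group 1 would add to it, and late visits would reduce it.

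The p-value and CI problem rests on the assumed placebo size of about 18,500, on 400 to 450 study recipients and on a 0.05 reading. Within those ranges the exact cut-offs shift by about one placebo event, but the disagreement between asymptotic and exact methods remains. It is not confined to one event in the study group. A reader might infer that the p-value is generally anti-conservative. It is not: the inflation is confined to a band of rates around 2.8e-4, where it reaches 8.9% against a nominal 5%.

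**What to change.** **p-value and CI.** In SAP 6.5.1, name one exact method for both: the exact unconditional method based on the same score statistic, with the CI at 2.5% per tail and p equal to twice the smaller one-sided exact p. They then agree by construction. Do not put a mid-p value beside that interval. At 1 vs 2 and 1 vs 3, mid-p is 0.036 and 0.047, while the one-sided exact p is 0.033 and 0.046, above 0.025, so the table would show p below 0.05 next to a CI that covers zero.

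**Window.** For Guillain-Barre syndrome and polyneuropathy, compare Day 1 through Day 29 by onset date in both arms, Day 29 being the earliest scheduled last-visit day. First confirm that C3671013 followed placebo recipients at least that long. List later cases through Day 43 separately, and state how many recipients were followed to Day 43. An analysis per person-time should not be offered as an alternative unless an exact method for rates is named with it.

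**Cost.** The change needs SAP wording, plus a recut of the C3671013 placebo counts by onset day, since a count and denominator alone will not do. The exact method is somewhat conservative. A Day 29 cut uses 450 × 29 = 13,050 person-days, so it moves 1,750 of 14,800 observed person-days (12%) to 4,025 of 17,075 (24%) from the comparison to the listing.
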